15. SAFETY AND TOLERABILITY ANALYSIS

The safety analysis population will be used for all safety outcomes. There will be no statistical comparisons between diagnosis or amyloid groups performed among the safety data.

15.1. Exposure to Flortaucipir

The net activity of flortaucipir injected (MBq) will be summarized using descriptive statistics in a table.

All exposure data will be presented in listings by visit to include:

- Date and time of the Injection
- Injection site
- Lot Number
- Total Dose Administered (mCi and MBq)
- Saline Flush Administered? (Yes/No)

15.1.1. Unit Conversion and Volume Calculation

Volume collected in mCi will be converted to MBq as follows:

- $MBq = 37 \times mCi$

15.2. Adverse Events

An AE is any undesirable experience occurring to a subject during a clinical trial, whether or not considered related to the study drug.

Treatment-emergent adverse events (TEAE) are any untoward medical occurrence associated with the use of a drug in humans, whether or not considered drug related. For the purposes of this study, untoward medical occurrences will be considered associated with the use of flortaucipir, and thus be reported as AEs, if they occur within 48 hours after administration of the PET tracer. AE that occur after the administration of study drug but outside the 48 hour reporting window will not be reported unless the investigator believes they are attributable to the drug.

The end of study for the purpose of AE reporting is defined as 48 hours after the administration of flortaucipir injection.

15.2.1. All AEs

All AEs will be coded using MedDRA Version 20.0. A summary of all AEs will be reported in a listing including:

- SOC
- PT
- Start Date/time
- End Date/time

- Severity
- Relationship to Flortaucipir (Yes/No)
- Relationship to Study Procedure (Yes/No)
- Serious? (Yes/No)
- Action Taken
- Event Resolution
- Lead to Death (Yes/No)

15.2.2. All TEAEs

A summary of TEAEs will be reported in the tables including:

- Number of all TEAE
- Number of subjects with at least one TEAE

The summary of TEAEs will be broken down further in descending frequency by SOC and PT, and by PT only in separate tables.

A subject will be counted once if the subject reported one or more events in a given level of summarization.

15.2.3. Severity

Severity is classed as mild/moderate/severe (increasing severity). TEAEs with a missing severity will be classified as severe. If a subject reports a TEAE more than once within that SOC/PT, the TEAE with the worst case severity will be used in the corresponding severity summaries.

TEAE severity will be reported in a table in the same manner as outlined in 15.2.2.

15.2.4. Relationship to Flortaucipir

Relationship, as indicated by the Investigator, is classed as related or unrelated to flortaucipir. TEAEs with a missing relationship to study medication will be regarded as related to flortaucipir. If a subject reports the same AE more than once within that SOC/PT, the AE with the worst case relationship to flortaucipir will be used in the corresponding relationship summaries.

TEAE relationship to flortaucipir will be reported in a table in the same manner as outlined in 15.2.2.

15.2.5. Relationship to Study Procedure

Relationship, as indicated by the investigator, is classed as related or unrelated to protocol procedure. TEAEs with a missing relationship to study procedure will be regarded as related to study procedure. If a subject reports the same AE more than once within that SOC/PT, the AE with the worst case relationship to study procedure will be used in the corresponding relationship summaries.

TEAE relationship to study procedure will be reported in a table in the same manner as outlined in 15.2.2.

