7.7.2. Adverse Event Definitions

Adverse Events

For reporting purposes, Avid will distinguish among pre-existing conditions, treatment-emergent adverse events and trial-emergent adverse events. Pre-existing conditions (i.e., undesirable experiences, signs or symptoms that begin prior to the Screening Visit) will be recorded on the medical history and/or physical exam eCRF pages. Signs and symptoms that are believed to be due to the pre-existing condition (started prior to dose of study medication) do not have to be recorded in the AEs section of the eCRF, unless there is an increase in frequency or severity. Additionally, signs or symptoms or changes in pre-existing conditions that occur outside the trial defined adverse event reporting period will be recorded in medical history.

An adverse event is any untoward medical occurrence associated with the use of a drug in humans, whether or not considered drug related. For the purposes of this study, untoward medical occurrences will be considered associated with the use of ¹⁸F-AV-1451, and thus be reported as adverse events, if they occur within 48 hours after ¹⁸F-AV-1451 administration. Adverse events associated with the use of ¹⁸F-AV-1451 injection will be recorded as treatment emergent. Adverse experiences that occur after administration of ¹⁸F-AV-1451 but outside the 48 hour reporting window will not be reported unless the investigator believes they are attributable to the drug.

In order to capture possible adverse effects of trial participation, trial-emergent adverse events will also be reported as any untoward medical occurrences occurring between the time of consent and the time of imaging, but not during the 48 hour window following the administration of ¹⁸F-AV-1451 injection.

The end of study for the purpose of adverse event reporting is defined as 48 hours after the administration of ¹⁸F-AV-1451.

Serious Adverse Event (SAE)

An SAE is an AE that results in one of the following outcomes or constitutes one of the following events:

- Death;
- Initial or prolonged inpatient hospitalization (other than that required by protocol; “social hospitalization” or any hospitalization for non-medical reasons does not constitute an SAE);
- A life-threatening experience (that is, immediate risk of dying);
- Persistent or significant disability/incapacity;
- Congenital anomaly/birth defect;
- Considered significant by the investigator for any other reason.

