8.3. Safety Analysis

Safety laboratory test results and vital signs measurements will be summarized by subject and by evaluation time point. Subjects whose laboratory values are outside the pre-determined upper and lower limits of normal will be identified and tabulated.

Adverse events including injection site reactions will be summarized in terms of number and percentage of subjects experiencing an AE. The summary will be further broken down by system organ class (SOC) and preferred term using Medical Dictionary for Regulatory Activities (MedDRA) terms. Adverse events will also be presented by severity, relationship to treatment and seriousness. All subjects who experience SAEs or who discontinue due to AEs will be summarized.

Discontinuation

All subjects who discontinue participation prior to completing the study will be listed and their discontinuation reasons will be tabulated.

Laboratory Data

Subjects whose laboratory values are outside threshold values will be identified and tabulated.

Vital Signs

Vital signs measurements will be summarized by subject and by evaluation time point.

ECG

Any subjects showing QTc > 500 will be highlighted.

8.4. ¹⁸F-AV-1451 Image Analysis

All ¹⁸F-AV-1451 PET images obtained starting at approximately 80 minutes post injection will be analyzed. The ¹⁸F-AV-1451 PET images will be spatially normalized to standard stereotactic atlas space using MNI brain atlas. The uptake in tau protein rich brain regions will be assessed with regions of interest (ROI, designed in MNI brain atlas) in terms for standard uptake value ratio (SUV_r, normalized by cerebellar uptake). The spatially normalized images and the measured SUV_r values will be used to accordingly to accomplish the study objectives.

Exploratory analysis will include co-registration of MRI to the ¹⁸F-AV-1451 PET images for ROI creation and/or partial volume correction of ¹⁸F-AV-1451 PET images using anatomical information from MRI data.

Additional analyses may explore various voxel and threshold based approaches.

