16. INTERIM ANALYSES

There is no interim analysis planned for this study.

APPENDIX I: ALGORITHMS TO HANDLE MISSING AND PARTIAL DATES**1.1.MISSING AND PARTIAL CONCOMITANT AND OTHER
MEDICATION START AND STOP DATES**

CONMED START DATE	CONMED STOP DATE	ACTION
Known	Known	If stop date < study med date, assign as prior If stop date ≥ study med date, assign as concomitant
	Partial	Impute stop date as latest possible date (i.e. last day of month if day unknown or 31 st December if day and month are unknown), then: If stop date < study med date, assign as prior If stop date ≥ study med date and start date, assign as concomitant
	Missing	If stop date is missing could never be assumed a prior medication
Partial	Known	Impute start date as earliest possible date (i.e. first day of month if day unknown or 1 st January if day and month are unknown), then: If stop date < study med date, assign as prior If stop date ≥ study med date and start date, assign as concomitant
	Partial	Impute start date as earliest possible date (i.e. first day of month if day unknown or 1 st January if day and month are unknown) and impute stop date as latest possible date (i.e. last day of month if day unknown or 31 st December if day and month are unknown), then: If stop date < study med date, assign as prior If stop date ≥ study med date and start date, assign as concomitant
	Missing	Impute start date as earliest possible date (i.e. first day of month if day unknown or 1 st January if day and month are unknown), then: If stop date is missing could never be assumed a prior medication
Missing	Known	If stop date < study med start date, assign as prior If stop date ≥ study med start date, assign as concomitant

CONMED START DATE	CONMED STOP DATE	ACTION
	Partial	Impute stop date as latest possible date (i.e. last day of month if day unknown or 31 st December if day and month are unknown), then: If stop date < study med date, assign as prior If stop date ≥ study med date, assign as concomitant
	Missing	Assign as concomitant

1.2.MISSING AND PARTIAL AE ONSET DATES

If the AE onset dates are missing, then the most conservative approach will be used to decide if the AE is TEAE or not, as detailed in the table below:

AE ONSET DATE/TIME	AE STOP DATE/TIME	ACTION
Partial, but known components show that it cannot be on or after an injection date/time and within 48 hours post-injection	Known	Not TEAE
	Partial	Not TEAE
	Missing	Not TEAE

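### Every AE table in the SAP is limited to TEAEs, so events with known onset between consent and injection are listed but not tabulated, and the status of late tracer-attributed events is unsettled

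*SAP*

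**What the plan says.** **Protocol.** Section 7.7.2 defines two reportable classes after consent. Treatment-emergent events fall within 48 hours of the injection. In addition, "trial-emergent adverse events will also be reported as any untoward medical occurrences occurring between the time of consent and the time of imaging", leaving out the 48-hour window; the stated purpose is to pick up harm from taking part in the trial. Section 8.3 says that AEs "will be summarized in terms of number and percentage of subjects experiencing an AE", with further presentation by severity, relationship and seriousness, and that all subjects with serious events will be summarized. None of this is limited to TEAEs. Section 7.7.4 collects a serious event between consent and dosing only if the investigator thinks a protocol procedure may have caused it.

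**SAP.** Section 15.2 sets the TEAE window: "untoward medical occurrences will be considered associated with the use of flortaucipir, and thus be reported as AEs, if they occur within 48 hours" after the tracer is given. The same paragraph adds that events "outside the 48 hour reporting window will not be reported unless the investigator believes they are attributable to the drug". Section 15.2.1 covers the full set: "A summary of all AEs will be reported in a listing including" relationship to study procedure and seriousness, among other items. Sections 15.2.2 to 15.2.7 then specify tables, all on TEAEs. For procedures, "TEAE relationship to study procedure will be reported in a table". The term trial-emergent does not occur in these sections, and section 5 records only one change from the protocol, the move to the MUBADA measure.

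**The concern.** The procedure-relatedness table is where a reader will look for harm caused by study procedures. MRI is done before the imaging visit (SAP 4.2) and safety labs are taken before injection (SAP 4.1), so most events they cause begin before the injection and cannot be TEAEs if their onset is properly dated. The same holds for pre-dose serious events: protocol 7.7.4 keeps only those suspected of being caused by a procedure, yet they enter neither the procedure table nor the serious table.

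There is a second problem at the other end of the window. An event judged attributable to the tracer after 48 hours is to be reported, but the SAP does not say whether it enters the tables that describe tracer-related harm. At stake is whether the tabulated rates of procedure-related, serious and tracer-related events mean what a reader will take them to mean.

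**Working it through.** No arithmetic applies and the plan gives no figure to reproduce. The check lists each planned AE output with the events it covers, then classifies typical events under SAP 15.2 and Appendix I, 1.2.

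**Step 1: outputs.**

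| SAP section | Output | Events covered |
|---|---|---|
| 15.2.1 | Listing | All AEs |
| 15.2.2 | Tables: overall, SOC and PT, PT only | TEAEs |
| 15.2.3 | Table: severity | TEAEs |
| 15.2.4 | Table: relationship to flortaucipir | TEAEs |
| 15.2.5 | Table: relationship to procedure | TEAEs |
| 15.2.6 | Table: serious events | TEAEs |
| 15.2.7 | Table: events leading to death | TEAEs |

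No table covers anything but TEAEs.

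**Step 2: classification of events.**

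| Event | Status | Where it appears |
|---|---|---|
| MRI or blood-draw event, known onset before injection | Not a TEAE | Listing only |
| Pre-dose serious event suspected of being procedure-caused, known onset | Not a TEAE | Listing only; absent from 15.2.5 and 15.2.6 |
| Bruise from a same-day blood draw, onset after injection and within 48 hours | TEAE | Tables |
| Pre-injection procedure event, onset missing or partial and possibly inside the window, stop missing or on/after injection | TEAE by Appendix 1.2 | Tables |
| Catheter, injection or PET event, onset within 48 hours after injection | TEAE | Tables |
| Attributed to the tracer, after 48 hours, onset fully known | Not stated | Listing; tables unclear |
| Attributed to the tracer, after 48 hours, partial onset that rules out the window | Not a TEAE by Appendix 1.2 | Listing only |

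The last row follows from the first entry in Appendix 1.2, "Partial, but known components show that it cannot be on or after an injection date/time and within 48 hours post-injection", which leads to exclusion whatever the stop date and makes no exception for attribution. The row above it is open because Appendix 1.2 deals only with missing or partial dates, and 15.2 says such events are reported without saying as what.

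**Step 3: population.** SAP 7.1.2 limits the safety population to injected subjects, and SAP 15 applies that population to all safety outcomes. Read literally, a subject who has an event at the MRI visit and is never injected is outside even the 15.2.1 listing.

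**Step 4: are the data there?** The flow charts (protocol 11.2, SAP 3.2.1) collect AEs and serious AEs at the screening and MRI visits. The consent-to-injection interval is preferably within 30 days of the final A05 visit and may reach 3 months (protocol 7.1.3), if consent is taken at that visit as planned.

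**The case against.** The best defence is that nothing recorded is hidden. The 15.2.1 listing shows each AE with its dates, procedure relationship and seriousness, and a listing is a form of reporting, which is all that protocol 7.7.2 asks for trial-emergent events. The disposition table (SAP section 8) represents the whole screened population and counts adverse event and death among the discontinuation reasons. The pre-injection period holds only an ECG, one lab collection and one MRI, so its length overstates the exposure to procedures. Safety is not the primary objective.

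Most of this stands, and it limits the size of the point. It does not remove it: protocol 8.3 promises counts and percentages and a summary of all subjects with serious events, and a listing gives neither. Disposition counts cover only events that ended participation.

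A reader might also infer that the procedure table can hold no MRI or blood-draw events at all. The documents do not support that. TEAE status depends on when an event starts, not on what caused it, so same-day draws with later onset and events with missing or ambiguous dates can enter. Nor do the documents show that late tracer-attributed events are always excluded. The attribution clause sits in the paragraph that defines TEAEs and can be read as admitting them; only the partial-date case is clearly out. That case is a narrow one, though late events are foreseeable, since the follow-up call is made no earlier than 48 hours and asks for new events.

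**Conclusion.** The point holds in this form. Followed as written, the SAP leaves AEs with known onset between consent and injection out of every table, including the procedure, serious and fatal ones. That is an undeclared departure from protocol 8.3. It also leaves the TEAE status of late tracer-attributed events unclear in 15.2 and excludes one subset of them in Appendix 1.2.

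For injected subjects the events are untabulated, not lost. For subjects never injected, a literal reading of the safety population removes them from the AE listing as well. The documents give no AE rates, so the number affected cannot be estimated; it is probably small. The primary imaging analysis is not touched. This is a safety-reporting correction worth making before the tables are programmed.

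**What to change.** 1. In SAP 15.2, define trial-emergent AEs (consent to injection). Add a count and percentage table of them by procedure relationship and seriousness, based on all consented subjects, including those never injected. SAP 7.1.2 and the opening of section 15 need a matching exception.
2. Base the 15.2.5 procedure table and the 15.2.6 and 15.2.7 summaries on all recorded AEs from consent, split into before and after injection. Add a footnote that protocol 7.7.4 collects pre-dose serious events only when a procedure may have caused them, so the pre-injection serious counts are not a complete census.
3. State in 15.2 and in Appendix I, 1.2 that an AE after 48 hours attributed to flortaucipir counts in the TEAE and relatedness tables, so that the partial-date rule no longer overrides the attribution clause.
4. Record in SAP section 5 any difference from protocol 8.3 that remains.

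The cost is some SAP wording and one or two small extra tables. No new data collection is needed.

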15.2.6. Serious Adverse Events

Serious TEAEs will be summarized in a similar manner as described in Section 15.2.2. If a subject reported more than one serious TEAE with the same SOC or PT, the TEAE will be counted only once in that SOC or PT.

15.2.7. Adverse Events Leading to Death

TEAEs leading to death will be summarized in a similar manner as described in Section 15.2.2.

15.2.8. Missing and Partial AE Onset Dates

See appendix 1.2 for specific algorithms to impute missing start and stop dates

15.3. Vital Signs

The following vital signs are collected at two time points – *Immediately Prior to (within 5 minutes) Flortaucipir Injection* and *Prior to Discharge* - during the Flortaucipir Imaging Visit. *Immediately Prior to Injection* will be considered the baseline value for all vital sign change calculations

- Supine Systolic Blood Pressure (mmHg)
- Supine Diastolic Blood Pressure (mmHg)
- Supine Pulse Rate (bpm)
- Respiratory Rate (breaths/min)

The data from each time point, along with calculated CFB, as defined as the difference from the *Prior to Injection* to *Prior to Discharge* values will be summarized by diagnosis groups in a table using descriptive statistics. A paired t-test will be performed on the aggregate data of each vital sign to assess if any significant changes occurred.

Vital signs and changes (where applicable) will be presented in a listing along with the following information.

- Time point
- Were Vital Signs Collected
- Collection Date/time

15.3.1. Potentially Clinically Significant Vital Sign Changes

Vital sign at visit and CFB will be monitored for potentially clinically significance (PCS). Below are the PCS criteria.

Table 2: Potentially Clinically Significant Criteria

Parameter		Potentially Clinically Significant Criteria	
		Low	High
Vital Sign			
Systolic blood pressure	mmHg	≤ 90 and ≥ 20 decrease	≥ 180 and ≥ 20 increase
Diastolic blood pressure	mmHg	≤ 50 and ≥ 15 decrease	≥ 105 and ≥ 15 increase
Pulse rate	bpm	≤ 50 and ≥ 15 decrease	≥ 120 and ≥ 15 increase
Respiration rate	Breaths/min	≤ 10	

15.4. Follow-up Telephone Contact Data

The follow-up safety data will be presented in a listing and include:

- Was Contact Made? (Yes/No); Explanation, if No
- Date/time of Follow-up Assessment
- Any AE Reported? (Yes/No)

16. INTERIM ANALYSES

There is no interim analysis planned for this study.

APPENDIX I: ALGORITHMS TO HANDLE MISSING AND PARTIAL DATES**1.1.MISSING AND PARTIAL CONCOMITANT AND OTHER
MEDICATION START AND STOP DATES**

CONMED START DATE	CONMED STOP DATE	ACTION
Known	Known	If stop date < study med date, assign as prior If stop date ≥ study med date, assign as concomitant
	Partial	Impute stop date as latest possible date (i.e. last day of month if day unknown or 31 st December if day and month are unknown), then: If stop date < study med date, assign as prior If stop date ≥ study med date and start date, assign as concomitant
	Missing	If stop date is missing could never be assumed a prior medication
Partial	Known	Impute start date as earliest possible date (i.e. first day of month if day unknown or 1 st January if day and month are unknown), then: If stop date < study med date, assign as prior If stop date ≥ study med date and start date, assign as concomitant
	Partial	Impute start date as earliest possible date (i.e. first day of month if day unknown or 1 st January if day and month are unknown) and impute stop date as latest possible date (i.e. last day of month if day unknown or 31 st December if day and month are unknown), then: If stop date < study med date, assign as prior If stop date ≥ study med date and start date, assign as concomitant
	Missing	Impute start date as earliest possible date (i.e. first day of month if day unknown or 1 st January if day and month are unknown), then: If stop date is missing could never be assumed a prior medication
Missing	Known	If stop date < study med start date, assign as prior If stop date ≥ study med start date, assign as concomitant

CONMED START DATE	CONMED STOP DATE	ACTION
	Partial	Impute stop date as latest possible date (i.e. last day of month if day unknown or 31 st December if day and month are unknown), then: If stop date < study med date, assign as prior If stop date ≥ study med date, assign as concomitant
	Missing	Assign as concomitant

1.2.MISSING AND PARTIAL AE ONSET DATES

If the AE onset dates are missing, then the most conservative approach will be used to decide if the AE is TEAE or not, as detailed in the table below:

AE ONSET DATE/TIME	AE STOP DATE/TIME	ACTION
Partial, but known components show that it cannot be on or after an injection date/time and within 48 hours post-injection	Known	Not TEAE
	Partial	Not TEAE
	Missing	Not TEAE
Partial, could be on or after an injection date/time and within 48 hours post-injection	Known	If stop date/time < flortaucipir injection date/time, then not TEAE If stop date/time >= flortaucipir injection date/time, then TEAE
	Partial	Impute stop date as latest possible date (i.e. 59 if minutes unknown or 23:59 if hours and minutes unknown; last day of month if day unknown or 31st December if day and month unknown), then: If stop date/time < flortaucipir injection date/time, then not TEAE If stop date/time >= flortaucipir injection date/time, then TEAE

AE ONSET DATE/TIME	AE STOP DATE/TIME	ACTION
	Missing	Assumed TEAE
Missing	Known	
If stop date/time < flortaucipir injection date/time, then not TEAE
 
If stop date/time >= flortaucipir injection date/time, then TEAE

	Partial	
Impute stop date as latest possible date (i.e. 59 if minutes unknown or 23:59 if hours and minutes unknown; last day of month if day unknown or 31st December if day and month unknown), then:
 
If stop date/time < flortaucipir injection date/time, then not TEAE
 
If stop date/time >= flortaucipir injection date/time, then TEAE

	Missing	Assumed TEAE
